9.5. Study Size

The sample size for this study is fixed by the duration of the observation window. All subjects who meet the inclusion/exclusion criteria will be included in the analyses.

Feasibility analyses from 31 August 2022- 16 January 2023 confirmed the availability of data to identify vaccinated subjects. Table 5 below shows the estimated number of patients in each group.

Table 5. Estimated Number of Patients in Each Vaccination Exposure Group

	Group 1: Same Day	Group 2: COVID- 19 alone	Group 3: Flu alone	CCl [REDACTED]
18-64	244,864	144,695	772,418	CCl [REDACTED]
65+	382,806	225,842	1,351,093	CCl [REDACTED]

Composite COVID-19 hospitalizations/UC/ED

For 65+, and the Group 1 vs Group 2 comparison of the COVID-19 related composite hospitalizations/ED/UC endpoint, we assume the percentage of patients in Group 1 will be 63% and the expected percentage of patients in Group 1 and Group 2 with an event overall will be 0.56%. If we use a non-inferiority margin of 1.15 for the upper bound of the 95% CI, 1-sided alpha of 0.025, and 80% power, and an expected HR of 1, then we would need 1,724 events resulting in 193,548 patients in Group 1, and 113,671 in Group 2, which meets our current estimated sample size.¹⁹

For 18-64, and the Group 1 vs Group 2 comparison of the COVID-related composite hospitalizations/ED/UC endpoint, we assume the percentage of patients in Group 1 will be 63% and the expected percentage of patients in Group 1 and Group 2 with an event overall will be 0.066%. If we use a non-inferiority margin of 1.15 for the upper bound of the 95% CI, 1-sided alpha of 0.025, and 80% power, and an expected HR of 1, then we would need 1,638,003 in Group 1, and 962,002 in Group 2, which does not meet our current estimated sample size.

Composite influenza hospitalizations/UC/ED

For 65+ and for the Group 1 vs Group 3 comparison of the flu-related composite hospitalizations/UC/ED endpoint, we assume the percentage of patients in Group 1 will be 23% and the expected percentage of patients in Group 1 and Group 3 with the endpoint overall will be 0.3%. If we use a non-inferiority margin of 1.15 for the upper bound of the 95% CI, 1-sided alpha of 0.025, and 80% power, and an expected HR of 1, then we would need 2,269 events resulting in 176,179 in Group 1, and 589,817 in Group 3, which meets our current estimated sample size.

For 18-64 and for the Group 1 vs Group 3 comparison of the flu-related composite hospitalizations/UC/ED endpoint, we assume the percentage of patients in Group 1 will be 23% and the expected percentage of patients in Group 1 and Group 3 with the endpoint overall will be 0.09%. If we use a non-inferiority margin of 1.15 for the upper bound of the 95% CI, 1-sided alpha of 0.025, and 80% power, and an expected HR of 1, then we would need 574,716 in Group 1, and 1,924,050 in Group 3, which does not meet our current estimated sample size.

The inputs to the sample size calculations are based on unadjusted estimates across both exposure groups, and there is the possibility of confounding. After adjustment, it is likely that endpoint estimates may be closer together, thus increasing our power for non-inferiority analyses.

COVID-19 Outpatient Visits

For 65+, and the Group 1 vs Group 2 comparison of the COVID-19 related outpatient visits endpoint, we assume the expected percentage of patients in Group 1 and Group 2 with an event overall will be 1.77%. If we use a non-inferiority margin of 1.15 for the upper bound of the 95% CI, 1-sided alpha of 0.025, and 80% power, and an expected HR of 1, then we would need 61,218 in Group 1, and 35,954 in Group 2, which meets our current estimated sample size.

For 18-64, and the Group 1 vs Group 2 comparison of the COVID-19 related outpatient visits endpoint, we assume the expected percentage of patients in Group 1 and Group 2 with an event overall will be 1.47%. If we use a non-inferiority margin of 1.15 for the upper bound of the 95% CI, 1-sided alpha of 0.025, and 80% power, and an expected HR of 1, then we would need 73,767 in Group 1, and 43,324 in Group 2, which meets our current estimated sample size.

Influenza Outpatient Visits

For 65+ and for the Group 1 vs Group 3 comparison of the flu-related outpatient visits endpoint, we assume the expected percentage of patients in Group 1 and Group 3 with the endpoint overall will be 0.47%. If we use a non-inferiority margin of 1.15 for the upper bound of the 95% CI, 1-sided alpha of 0.025, and 80% power, and an expected HR of 1, then we would need 110,467 in Group 1, and 369,822 in Group 3, which meets our current estimated sample size.

For 18-64 and for the Group 1 vs Group 3 comparison of the flu-related outpatient visits endpoint, we assume the expected percentage of patients in Group 1 and Group 3 with the endpoint overall will be 0.76%. If we use a non-inferiority margin of 1.15 for the upper bound of the 95% CI, 1-sided alpha of 0.025, and 80% power, and an expected HR of 1, then we would need 68,854 in Group 1, and 230,511 in Group 3, which meets our current estimated sample size.

9.6. Data Management

All Optum claims structured data described above are stored within Pfizer's data infrastructure. Data are queried and analyzed using SAS. The data are only accessible to Pfizer colleagues who have been trained and approved to access Pfizer's data warehouse.

9.7. Data Analysis

There is not a separate Statistical Analysis Plan document for this study. All methodology for summary and statistical analyses of data collected in this study is contained in this section. All computations and generation of tables will be performed using Statistical Analysis System (SAS) version 9.4 or higher (SAS Institute, Cary, NC, US).

All analyses will be conducted for the following age subgroups: 18-64 and 65+.

Descriptive statistics will be presented to describe baseline characteristics by vaccination exposure group. Baseline characteristics will be described by frequency distribution for categorical variables while continuous variables expressed in terms of their mean and standard deviation or median and interquartile range (IQR) as appropriate. In general, missing or unavailable data will not be imputed and data will be analyzed as they are recorded in the database.

To account for imbalance in patient characteristics between the vaccine exposure groups, 2 separate logistic regression models will be used to create a propensity score used to calculate an inverse probability of treatment weights (IPTW). The two models will be as follows: Same day vs COVID-19 alone, and separately Same day vs Flu alone. Weights will be stabilized to avoid exertion of outliers, and we will further evaluate whether there is a need to truncate at the 1st and 99th percentile. Covariate balance before and after weighting will be assessed using standardized mean differences, separately for the same day/COVID-19 alone and Same day/flu alone comparisons. All variables listed in “[Covariates](#)” section with model specification instructions will be included in the score. If there are model convergence issues, changes in model specification may occur (eg, dropping variables with very low prevalence, categories may be collapsed further etc). Variables with residual imbalance will be included in the model for further adjustment.

Each outcome will be assessed separately. Experiencing one disease specific outcome is not a censoring criteria for the other disease (ie, having a COVID-19 outpatient diagnosis is not a censoring event for the influenza endpoints). Weighted cumulative incidence curves will be used to describe the occurrence of each outcome separately over the entire follow-up period. Given the relatively short follow-up time, we expect small numbers of deaths. Therefore, regular Cox proportional hazards models will be used to estimate HRs and 95% CI for each outcome separately. If we find that death is more common than anticipated, we will consider using Fine and Gray's proportional subdistribution hazards models to account for the competing risk of death. Models for the following vaccine group/outcome combinations will be assessed:

- Same day/COVID-19 only:
 - All-cause hospitalization, composite COVID-19 hospitalization/ED/UC (any position), COVID-19 hospitalization (any position, primary position), COVID-19 ED/UC, COVID-19 outpatient
- Same day/Flu only:
 - All-cause hospitalization, composite flu-hospitalization/ED/UC (any position), flu-hospitalization (any position, primary position), flu ED/UC, flu outpatient.

CCI

Sensitivity Analysis

For disease specific endpoints, we will conduct a sensitivity analysis whereby an additional censoring criteria will be applied. For COVID-19 specific endpoints, we will censor for Paxlovid dispensing. For influenza specific endpoints, we will censor for any of the following influenza treatment dispensing (Oseltamivir phosphate, Zanamivir, Peramivir, Baloxavir marboxil).

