9.3.2. Outcomes

All outcomes will be assessed starting on Day 15. All hospitalization related outcomes in the table below will be ascertained using acute facility stays only. Inpatient stays classified as skilled nursing facility or rehabilitation will not be used. COVID-19 and flu hospitalizations will be assessed in any position and in the primary position to mitigate possibility of hospitalization with the disease versus for the disease.

COVID-19 related endpoints will be identified using the following ICD-10-CM diagnosis code: U07.1.

Influenza will be identified using the following ICD-10-CM diagnosis codes: J09.X, J10.X, J11.X.

We will evaluate three negative control outcomes. These outcomes are unrelated to vaccination and likely share similar confounding patterns for health-seeking behaviors. These negative controls have been used in other studies of comparative VE of influenza vaccines or COVID-19 VE.¹³⁻¹⁵ Urinary tract infection and accidental injury are outcomes that could differentiate patients who seek medical care versus those who do not, and is likely a better choice of outcome for younger adults. Hospitalization in the first 14 days (ie, among recently vaccinated) uses time as a negative control, in that the vaccine likely could not biologically prevent health events until adequate levels of immunity has been achieved.

Table 2. Outcome Variables

Variable	Role	Operational definition
All-cause hospitalization	Outcome	An inpatient (acute facility) claim that meets the following criteria: 
1. Occurs >14 days after the patient's first mRNA bivalent COVID-19 or influenza vaccine dose during the study period.2. Place of service = 21.3. Non-null confinement ID.4. tos_cd = 'FAC_IP.ACUTE'.
Composite COVID-19 related hospitalization/ED/UC (any position)	Outcome	An inpatient (acute facility) claim that meets the following criteria: 
1. Occurs >14 days after the patient's first mRNA bivalent COVID-19 or influenza vaccine dose during the study period.2. Place of service = 21.

PFIZER CONFIDENTIAL

Table 2. Outcome Variables

Variable	Role	Operational definition

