9.3.4. Covariates

Table 4. Covariates		
Variable	Role	Operational definition
Age	Patient Characteristics, Subgroup	
The number of years between the index date and the patient birth year. Age will be reported in the following categories: 18-64 and 65+.
 
Continuous statistics including mean, standard deviation (SD), median (Q1-Q3), minimum, and maximum, will also be summarized.
 
Model specification: continuous linear

Sex	Patient Characteristics	
Sex will be reported as Male ('M'), Female ('F'), and Unknown
 
Model specification: categorical

US Geographic Region	Patient Characteristics	
US geographic region will be derived from the patient state and categorized into the following:
 
Northeast – Connecticut, Maine, Massachusetts, New Hampshire, Rhode Island, Vermont, New Jersey, New York, Pennsylvania
 
Midwest – Indiana, Illinois, Michigan, Ohio, Wisconsin, Iowa, Kansas, Minnesota, Missouri, Nebraska, North Dakota, South Dakota
 
South – Delaware, District of Columbia, Florida, Georgia, Maryland, North Carolina, South Carolina, Virginia, West Virginia, Alabama, Kentucky, Mississippi, Tennessee, Arkansas, Louisiana, Oklahoma, Texas
 
West – Arizona, Colorado, Idaho, New Mexico, Montana, Utah, Nevada, Wyoming, Alaska, California, Hawaii, Oregon, Washington
 
Other/unknown – Puerto Rico/unknown region
 
Model specification: categorical

Charleston Comorbidity Index (CCI)	Patient Characteristics	
Charleston Comorbidity Index score will be measured during the 12 month baseline period before index and will be reported in the following categories: 0, 1, and 2+. Continuous statistics including mean, standard deviation (SD), median (Q1-Q3), minimum, and maximum, will also be summarized.
 
Model specification: categorical (0,1,2+)

Prior Pneumonia or respiratory failure	Patient Characteristics	Any code (any setting) within the 1 year baseline for any type of pneumonia or respiratory failure
Prior heart disease	Patient Characteristics	Any code (any setting) within the 1 year baseline for heart disease
Prior asthma	Patient Characteristics	Any code (any setting) within the 1 year baseline for asthma

PFIZER CONFIDENTIAL

Table 4. Covariates

Variable	Role	Operational definition
Prior chronic lung disease	Patient Characteristics	Any code (any setting) within the 1 year baseline for chronic lung disease

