9.8. Quality Control

Data in Optum's claims database are collected monthly in an electronic format. Analyses are programmed according to the specifications in the protocol and documented in a programming plan. All analyses will be performed internally and according to Pfizer analytic standards, including double programming to ensure quality control. All quality checks are documented in the programming plan.

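### As written, the propensity-score inclusion rule leaves six defined comorbidity covariates out of both scores, possibly by oversight; a yes/no specification for each would close the gap.

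*Combined protocol and SAP*

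**What the plan says.** Section 9.7 describes two logistic propensity models, same day versus COVID-19 alone and same day versus flu alone, from which the inverse probability weights are built. The variables in the Covariates "section with model specification instructions will be included in the score".

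Table 4 in Section 9.3.4 defines the covariates. Most rows end with a model specification line. The comorbidity rows at issue stop at the definition, for example "Any code (any setting) within the 1 year baseline for heart disease" and "Any code (any setting) within the 1 year baseline for asthma".

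Section 9.7 then gives a check and a fallback: "Covariate balance before and after weighting will be assessed using standardized mean differences", and "Variables with residual imbalance will be included in the model for further adjustment".

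The section also says there is no separate SAP and that "All methodology for summary and statistical analyses of data collected in this study is contained in this section". Section 9.8 adds: "Analyses are programmed according to the specifications in the protocol and documented in a programming plan".

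**The concern.** The weights are the study's main protection against confounding, and Section 9.5 itself acknowledges that its unadjusted inputs may be confounded. The six conditions are plausible causes of hospitalization and of emergency or urgent care use, and they may differ between people who take both vaccines on one day and people who take one. The protocol defined them as covariates, yet its rule does not admit them to the score.

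Nothing in the text says this was intended. Where the protocol keeps a covariate out of the model on purpose, it labels the row, and these six rows have no label. If the omission is an oversight and the rule is programmed as written, the weighted hazard ratios may keep confounding that already-defined variables could reduce.

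**Working it through.** No design figure is in dispute. The check is a row count of Table 4 against the inclusion rule in Section 9.7.

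**Step 1. Sort the 35 rows of Table 4.**

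| Status in Table 4 | Rows | Which |
|---|---|---|
| Has a model specification | 26 | Age, sex, region, comorbidity index, index month, vaccination history, utilization terms and others |
| No specification, labelled as outside the model | 3 | Time from last COVID-19 dose; monovalent dose in the prior 60 days; type of index influenza vaccine |
| Neither | 6 | Prior pneumonia or respiratory failure; heart disease; asthma; chronic lung disease; diabetes; kidney disorders |

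26 + 3 + 6 = 35.

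**Step 2. Apply the rule.** Each score holds 26 of 35 covariates. With a specification added to the six rows it would hold 26 + 6 = 32, and the three left out would be exactly those the protocol labels.

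**Step 3. See what the score already carries for the six.**

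- The comorbidity index enters in categories 0, 1 and 2+. The shown text does not list its components, and the top category does not separate two conditions from many.
- The high-risk flag is one yes/no term over 21 listed conditions. It names chronic lung diseases, diabetes, chronic kidney disease and three types of heart condition. It also lists hypertension, overweight and obesity, smoking and mental health conditions. A patient with hypertension alone and a patient with heart failure, diabetes and kidney disease both score yes, so the flag can balance while the separate conditions do not. It does not name pneumonia or respiratory failure.
- Immunocompromised status, functional status, nursing-home and skilled-nursing markers, and prior outpatient and hospital use also enter, and should carry some of the same information.

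**Step 4. Ask what a bias could look like.** The documents give no prevalence of these conditions by group and no risk ratios, so the inputs here are assumed. For one omitted binary condition with prevalence p1 and p0 in the weighted groups, and risk ratio RR for the outcome given everything already in the score:

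bias factor = (1 + p1(RR − 1)) / (1 + p0(RR − 1))

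- 15% versus 14%, RR 1.5: 1.075 / 1.070 = 1.005. At RR 3: 1.30 / 1.28 = 1.016.
- 15% versus 12%, RR 1.5: 1.075 / 1.060 = 1.014. At RR 3: 1.30 / 1.24 = 1.048.
- 22.79% versus 15% (standardized difference 0.20), RR 3: 1.4558 / 1.30 = 1.12.

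The factor runs from about 1.005 to 1.12 depending only on what is assumed, and it can act in either direction. These figures describe the formula and are not estimates for this study.

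**The case against.** The strongest reply is that the plan already has a net for these variables. Section 9.7 assesses covariate balance without limiting it to the scored variables. The six sit in a section and a table both titled Covariates, and the narrowing to variables with a specification comes in a later sentence that governs entry to the score only. On that reading the six are checked and can be added if imbalanced. Adjustment after weighting points most naturally to the Cox model. This largely stands: a reader might infer that the plan makes no provision for the six, and the documents do not support that. What remains is that the reading is not explicit. The preceding sentences use 'model' for the propensity model, and no standardized-difference cut-off is given. The missing cut-off is a missing detail, and stating one would not by itself put the six in the score.

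The programming plan named in Section 9.8 could also record how the six enter. It was not available, but Section 9.7 claims to hold all the methodology, so the protocol should not depend on that plan.

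Three negative control outcomes are planned, described as follows: "These outcomes are unrelated to vaccination and likely share similar confounding patterns for health-seeking behaviors". They can signal residual confounding, but they cannot remove it.

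Further stronger readings do not hold:

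- That balance is not checked by comparison or age group. Section 9.7 assesses it separately for the two comparisons and runs all analyses for 18-64 and 65+.
- That asthma falls outside the high-risk flag. The shown text does not settle this, and the code lists may sit in annex material that was not available.
- That power or a non-inferiority conclusion is compromised. The 1.15 margin appears in Section 9.5, the visible part of Section 9.7 states no non-inferiority test, and any power loss would rest wholly on assumed inputs.

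**Conclusion.** The point holds as a gap in the text. The rule as written leaves six of 35 defined covariates out of both scores, and these six lack the label that marks the three deliberate exclusions. Whether this was intended cannot be told from the documents.

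The consequence is limited in what can be claimed. Partial substitutes are in the score, and the residual-imbalance step may pick up what they miss. The size and direction of any remaining bias cannot be derived from the documents, so the finding does not show that the hazard ratios are biased. The case for change rests on the inclusion rule, on the coarseness of the substitutes, and on the very low cost of including the six.

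**What to change.** Add a dichotomous (yes/no) model specification to the six Table 4 rows, so that they enter both scores.

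As a secondary clarification in Section 9.7, confirm that the standardized-difference check covers every Table 4 covariate, in or out of the score. Before any hazard ratio is seen, fix the cut-off that triggers further adjustment and name the model, propensity or Cox, that receives the imbalanced variables.

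The cost is protocol wording and six binary terms per score. The variables are already defined and need no new data. The smallest group in Table 5 has 144,695 patients, and Section 9.7 already allows low-prevalence terms to be dropped if a model fails to converge. The protocol is dated 26 April 2023 and data collection is planned to start on 05 May 2023, so the change can precede the analysis.

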9.4. Data Sources

Optum's Clininformatics Data Mart (CDM) comes from a database of administrative health claims for members of a large national managed care company affiliated with Optum. The database includes over 73 million unique lives (2007 through 2021). Clininformatics Data Mart is statistically de-identified under the Expert Determination method consistent with HIPAA and managed according to Optum customer data use agreements. These administrative claims submitted for payment by providers and pharmacies are verified, adjudicated, adjusted, and de-identified prior to inclusion. The Claims data comprises both commercial/employer sponsored plans and Medicare Advantage health plan data. This data covers ~30% of the national Medicare Advantage population. The population is geographically diverse, spanning all 50 states. In addition to medical claims and pharmacy claims, the Claims data includes tables with member eligibility and inpatient confinements. The Claims data also includes standard pricing for all medical claims, pharmacy claims, and inpatient confinements. Mortality is provided as month and year of death and is sourced from Centers for Medicare and Medicaid Services, Social Security Administration Death Master File, facility claims with inpatient death, discontinuation of coverage due to death and external obituary data.

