9.9. Limitations of the Research Methods

There are several limitations associated with this study. This analysis is from one insurer that provides employer-sponsored and Medicare Advantage coverage and thus may not generalize to other populations, such as traditional Medicare fee-for-service, other government insurance or uninsured. It is possible that some vaccines may be missing if patients received vaccine in a setting where an insurance claim was not filed (ie employer sponsored clinic or paid out of pocket). This may be more problematic for influenza vaccine for younger ages. This will only impact the singular vaccine groups (ie, COVID-19 alone or influenza alone). The healthcare claims data are collected for billing purposes and may be subject to misclassification, misdiagnosis, and underreporting. Additionally, for our medically attended COVID-19 endpoints, we do not have laboratory confirmation of the COVID-19 diagnosis, therefore it is possible that some patients are being diagnosed with symptoms alone or that we are missing positive cases due to at-home testing.

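### Insurance type (commercial/employer versus Medicare Advantage) is in neither propensity score, and not among the listed baseline or balance variables, although the database holds both plan types

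*Combined protocol and SAP*

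**What the plan says.** Section 9.7 describes the adjustment: "The two models will be as follows: Same day vs COVID-19 alone, and separately Same day vs Flu alone". Each score feeds inverse probability weights. Variables listed under Covariates "section with model specification instructions will be included in the score". Balance is then judged by standardized mean differences, and variables that remain imbalanced are added to the outcome model. Everything is run separately at 18-64 and 65+. Section 9.7 also says that there is no separate SAP.

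Table 4 (section 9.3.4) lists demographics, comorbidity, vaccination history, administration setting, facility residence, functional status and utilization. No row records insurance, plan or payer type, and no row of Table 4 is redacted.

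Section 9.4 says of the source: "The Claims data comprises both commercial/employer sponsored plans and Medicare Advantage health plan data". It adds that "the Claims data includes tables with member eligibility and inpatient confinements".

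Section 9.9 mentions coverage type once, as a limit on generalizability: "This analysis is from one insurer that provides employer-sponsored and Medicare Advantage coverage". Separately, it says that vaccines may be missed when given "in a setting where an insurance claim was not filed (ie employer sponsored clinic or paid out of pocket", and comments: "This may be more problematic for influenza vaccine for younger ages". It states that only the single-vaccine groups are affected.

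**The concern.** A baseline variable that splits the database into two kinds of member has no place in the adjustment. To confound within an age band it must relate to both exposure group and outcome.

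- **Exposure.** Section 9.9 implies that a same-day recipient with one unfiled vaccine is counted in a single-vaccine group. If employer clinics mainly serve people with employer coverage, the recorded groups could differ in plan mix. That step from clinic to coverage is an inference.
- **Outcome.** Plan type may track health, work status and care-seeking among people of similar age. The documents do not say so; it is an assumption.

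The plan's own diagnostics would not reveal a problem. Standardized mean differences and the residual-imbalance step act on listed covariates, and plan type is not listed. Event counts are large, so confidence intervals will be narrow and a shift of a few percent is not negligible beside them.

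**Working it through.** **1. The omission.** Set side by side: section 9.7 admits Table 4 variables with a model specification; Table 4 has no plan-type row; section 9.4 says that both plan types are present. Plan type therefore enters neither score. The unredacted sensitivity analysis in section 9.7 only adds censoring at antiviral dispensing.

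**2. The plan's own figure.** For the 65+ COVID-19 composite (section 9.5: margin 1.15, one-sided alpha 0.025, power 80%, 63% in Group 1), the Schoenfeld formula gives

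(1.960 + 0.842)² / (0.63 × 0.37 × (ln 1.15)²) = 1,724 events,

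which matches the protocol. Adding a covariate does not change this figure.

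**3. Possible shift in the HR.** For an omitted binary covariate with prevalence pA and pB in the two groups and residual hazard ratio k,

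bias factor = (1 + pA(k − 1)) / (1 + pB(k − 1)).

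All shares of Medicare Advantage and all values of k below are assumed, because the documents give none.

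| Age band | Assumed shares | k = 1.2 | k = 1.5 | k = 2 |
|---|---|---|---|---|
| 18-64 | 13% v 10% | 1.006 | 1.014 | 1.027 |
| 18-64 | 15% v 10% | 1.010 | 1.024 | 1.045 |
| 65+ | 90% v 85% | 1.009 | 1.018 | 1.027 |
| 65+ | 90% v 80% | 1.017 | 1.036 | 1.056 |

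Example: (1 + 0.90 × 1) / (1 + 0.80 × 1) = 1.90 / 1.80 = 1.056. The range is about 1 to 6%. If the groups are swapped, the factor is inverted.

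**4. What a 3% shift does to the 65+ COVID-19 composite.** Patients from Table 5: 382,806 + 225,842 = 608,648. Events at the 0.56% in section 9.5: 3,408. SE of log HR = 1 / √(3,408 × 0.63 × 0.37) = 0.0355. With bias factor b:

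- false non-inferiority at true HR 1.15 = Φ(−ln b / SE − 1.96)
- power at true HR 1 = Φ((ln 1.15 − ln b) / SE − 1.96)

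| b | False non-inferiority at HR 1.15 | Power at HR 1 |
|---|---|---|
| 1/1.03 (downward) | 13% | >99% |
| 1 | 2.5% | 98% |
| 1.03 (upward) | 0.3% | 87% |

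The SE treats patients as unweighted. Weighting would usually enlarge it, which would soften both effects.

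**The case against.** Several points on the other side stand.

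- A reader might infer that the protocol itself links employer coverage to misassignment between groups. It does not. Section 9.9 names where the vaccine was given and who paid, not the type of coverage.
- A reader might infer that the omission makes non-inferiority too easy to show. The documents do not support a direction. If unfiled employer-clinic vaccines moved lower-risk commercial members into the single-vaccine groups, the Same day HR would be biased upward, against non-inferiority. A downward bias would need another cause.
- A plan-type covariate does not reclassify anyone. Exposure misclassification from unfiled claims, which section 9.9 discloses, would remain within each plan type.
- Existing adjustment captures part of plan type: separate age bands and linear age, administration setting, nursing home and skilled nursing flags, functional status, a high-risk flag that includes disabilities, and utilization counts.
- The 1.15 margin appears in section 9.5 only. Section 9.7 plans HRs with 95% CIs and states no decision rule in its readable text.
- Section 9.4 says that eligibility tables exist. It does not say that plan type is a field in them.

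These points limit the claim without removing it. Whether the existing covariates suffice cannot be known while balance on plan type goes unexamined. Administration setting describes the recorded vaccine, not the missed one. Six comorbidity rows in Table 4 (pneumonia or respiratory failure, heart disease, asthma, chronic lung disease, diabetes, kidney disorders) carry no model specification, so on the rule in section 9.7 they do not enter the score in their own right.

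**Conclusion.** The point holds as an omission worth repairing, not as a demonstrated bias. Plan type is outside both scores, and the plan as written gives no view of its balance. Any residual confounding lies within age band and has unknown size and direction. The 1 to 6% range rests wholly on assumed shares and assumed residual ratios of 1.2 to 2. The 3% illustrations show only that shifts of that size matter beside an SE of 0.0355; they do not predict that such a shift will occur. Larger residual ratios, or claims about why people under 65 hold Medicare Advantage or people over 65 hold commercial cover, have no basis in the documents and are not relied on here.

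**What to change.** Add a row to Table 4: *Insurance type on index date (commercial / Medicare Advantage), from member eligibility data; model specification: categorical*. Include it in both propensity scores, and report it in the baseline and standardized-mean-difference tables for each age group. A run restricted to commercial members at 18-64 is an optional check on whether plan mix matters. If the sponsor prefers to leave plan type out of the scores, it should give the reason and still report its distribution by group.

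Cost: one more covariate and a re-run, assuming that the eligibility data carry plan type. No new data collection is needed. Unfiled-claim misclassification is a separate problem that this change does not solve.
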